6.5. Exploratory Endpoints

6.5.1. List of Exploratory Endpoints

PPD [Redacted]

6.5.2. Analysis Methods for Exploratory Endpoints

PPD [Redacted]

6.6. Changes From Protocol-Specified Efficacy Analyses

PPD [Redacted]

PPD

[Redacted]

[Redacted]

[Redacted]

[Redacted]

[Redacted]

[Redacted]

7. SAFETY ANALYSES

7.1. Adverse Events and Deaths

7.1.1. Adverse Event Dictionary

Clinical and laboratory adverse events (AEs) will be coded using the current version of MedDRA 20.1. System organ class (SOC), high-level group term (HLGT), high-level term (HLT), preferred term (PT), and lower-level term (LLT) will be provided in the AE dataset.

7.1.2. Adverse Event Severity

Adverse events are graded by the investigator as Grade 1, 2, 3, 4, or 5 according to toxicity criteria specified in the protocol. The severity grade of events for which the investigator did not record severity will be categorized as “missing” for tabular summaries and data listings. The missing category will be listed last in summary presentation.

Severity of adverse events will be determined by the investigator as mild, moderate, or severe. The severity of events for which the investigator did not record severity will be categorized as “missing” for tabular summaries and data listings. The missing category will be listed last in summary presentation.

7.1.3. Relationship of Adverse Events to Study Drug

Related AEs are those for which the investigator selected “Related” on the AE case report form (CRF) to the question of “Related to Study Treatment.” Relatedness will always default to the investigator’s choice, not that of the medical monitor. Events for which the investigator did not record relationship to study drug will be considered related to study drug for summary purposes. However, by-subject data listings will show the relationship as missing.

7.1.4. Serious Adverse Events

Serious adverse events (SAEs) will be identified and captured as SAEs if AEs met the definitions of SAE specified in the study protocol. Serious adverse events captured and stored in the clinical database will be reconciled with the SAE database from the Gilead Drug Safety and Public Health Department before data finalization.

7.1.5. Treatment-Emergent Adverse Events

7.1.5.1. Definition of Treatment-Emergent Adverse Events

Treatment-emergent adverse events (TEAEs) for the double-blind phase are defined as 1 or both of the following:

- Any AEs with an onset date on or after study drug or placebo start date and no later than earlier of 30 days after permanent discontinuation of study drug or placebo, or first dose date of ENTO in OLE phase, if any.
- Any AEs leading to premature discontinuation of study drug or placebo in the double-blind phase.

Treatment-emergent adverse events (TEAEs) for OLE phase are defined as 1 or both of the following

- Any AEs with an onset date on or after the OLE ENTO first dose date and no later than 30 days after permanent discontinuation of ENTO
- Any AEs leading to premature discontinuation of study drug or placebo in OLE.

7.1.5.2. Incomplete Dates

If the onset date of the AE is incomplete and the AE stop date is not prior to the first dosing date of study drug, then the month and year (or year alone if month is not recorded) of onset determine whether an AE is treatment emergent. The event is considered double blind phase treatment emergent if both of the following 2 criteria are met:

- The AE onset is the same as or after the month and year (or year) of the first double blind dosing date of study drug
- The AE onset date is the same as or before the month and year (or year) of the date corresponding to 30 days after the date of the last dose of study drug or placebo, or date of first study drug dose of OLE if any

The event is considered OLE phase treatment emergent if both of the following 2 criteria are met:

- The AE onset is the same as or after the month and year (or year) of the first OLE dosing date of study drug
- The AE onset date is the same as or before the month and year (or year) of the date corresponding to 30 days after the date of the last dose of study drug

An AE with completely missing onset and stop dates, or with the onset date missing and a stop date later than the first dosing date of study drug, will be considered to be treatment emergent. In addition, an AE with the onset date missing and incomplete stop date with the same or later month and year (or year alone if month is not recorded) as the first dosing date of study drug will be considered treatment emergent.

If the last study drug dosing date is missing, the latest date among the study drug end date, clinical visit date, laboratory sample collection date, weight and vital signs assessment date that occurred during the on-treatment period will be used.

7.1.6. Summaries of Adverse Events and Deaths

Treatment-emergent AEs will be summarized based on the Safety Analysis Set.

A brief summary of AEs will show, by treatment group, the number and percentage of subjects who (1) had any treatment-emergent AE, (2) had any Grade 3 or 4 treatment-emergent AE, (3) had any treatment-emergent treatment-related AE, (4) had any Grade 3 or 4 treatment-emergent treatment-related AE, (5) had any treatment-emergent SAE, (6) had any treatment-emergent treatment-related SAE, (7) had any treatment-emergent AE leading to permanent study drug discontinuation, (8) had any treatment-emergent SAE leading to permanent study drug discontinuation, (9) died during study.

Summaries (n and percentage of subjects) of treatment-emergent AEs (by SOC and PT) will be provided by treatment group using the Safety Analysis Set as follows:

- Summary of AEs
- All treatment-emergent AEs
- All treatment-emergent AEs by preferred term
- All Grade 3 or higher treatment-emergent AEs
- All Grade 3 or higher treatment-emergent AEs by preferred term
- All treatment-emergent treatment-related AEs
- All treatment-emergent treatment-related AEs by preferred term
- All Grade 3 or higher treatment-emergent treatment-related AEs
- All Grade 3 or higher treatment-emergent treatment-related AEs by preferred term
- All treatment-emergent SAEs
- All treatment-emergent SAEs by preferred term
- All treatment-emergent AEs leading to permanent study drug discontinuation
- All treatment-emergent AEs leading to permanent study drug discontinuation by preferred term

- All deaths

Multiple events will be counted once only per subject in each summary. For data presentation, SOC will be ordered alphabetically with PT sorted by decreasing total frequency. For summaries by severity grade, the most severe event will be selected. In addition to the presentation by SOC and PT, summaries of treatment-emergent AEs may be presented by PT only, ordered by decreasing total frequency.

In addition to the by-treatment summaries, data listings will be provided for the following:

- All AEs (with a variable indicating whether the event is treatment-emergent, treatment-related, SAE)
- All Grade 3 and 4 AEs (with a variable indicating whether the event is treatment-emergent, treatment-related, SAE)
- All SAEs (with a variable indicating whether the event is treatment-emergent, treatment-related)
- All Deaths (with a variable indicating whether the event is treatment-emergent, treatment-related, SAE)

All AEs leading to study drug discontinuation (with a variable indicating whether the event is treatment-related, SAE)

Tables of AE will be based on double-blind data. OLE AE will be included in the listings with a column indicating whether the AE was reported during the OLE phase.

Any AE, lab result, or vital sign occurring on or after the date of the first dose of OLE ENTO and no later than 30 days after permanent discontinuation of ENTO is deemed belonging to the OLE phase.

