7.2.2. Assessment of Severity

The severity of AEs will be graded using the modified CTCAE, version 4.03. For each episode, the highest grade attained should be reported.

If a CTCAE criterion does not exist, the investigator should use the grade or adjectives: Grade 1 (mild), Grade 2 (moderate), Grade 3 (severe), Grade 4 (life-threatening) or Grade 5 (fatal) to describe the maximum intensity of the adverse event. For purposes of consistency with the CTCAE, these intensity grades are defined in [Table 7-1](#) and [Appendix 7](#).

Table 7-1. Grading of Adverse Event Severity

Grade	Adjective	Description
Grade 1	Mild	Asymptomatic or mild symptoms; clinical or diagnostic observations only; intervention not indicated
Grade 2	Moderate	Local or noninvasive intervention indicated; limiting age-appropriate instrumental ADL
Grade 3	Severe	Severe or medically significant but not immediately life-threatening; hospitalization or prolongation of hospitalization indicated; disabling; limiting self-care ADL
Grade 4	Life-threatening	Urgent intervention indicated
Grade 5	Death	Death related AE

* Activities of Daily Living (ADL) Instrumental ADL refer to opening preparing meals, shopping for groceries or clothes, using the telephone, managing money, etc.

** Self-care ADL refer to bathing, dressing and undressing, feeding self, using the toilet, taking medications, and not bedridden

Table 7-2. Grading of Adverse Event Severity: Upper Respiratory

The only modification to the CTCAE criteria has been the addition of a Grade 1 upper respiratory infection as follows:

CTCAE v4.0 Term	Grade 1*	Grade 2	Grade 3	Grade 4	Grade 5	CTCAE v4.03 AE Term Definition
Upper respiratory infection	Mild symptoms; symptomatic relief (cough suppressant, decongestant, etc.)	Moderate symptoms; oral intervention indicated (e.g., antibiotic, antifungal, antiviral)	IV antibiotic, antifungal, or antiviral intervention indicated; radiologic, endoscopic, or operative intervention indicated	Life-threatening consequences; urgent intervention indicated	Death	A disorder characterized by an infectious process involving the upper respiratory tract (nose, paranasal sinuses, pharynx, larynx, or trachea).

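### SAP 7.1.6 limits two headline adverse-event rows and one listing to Grades 3 and 4, while the supporting tables include Grade 5, so the counts can disagree whenever there is a fatal event

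*SAP*

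**What the plan says.** **Grading scale.** SAP 7.1.2 states: "Adverse events are graded by the investigator as Grade 1, 2, 3, 4, or 5 according to toxicity criteria specified in the protocol". Protocol 7.2.2 defines the top of the scale as "Grade 4 (life-threatening) or Grade 5 (fatal") and gives the recording rule: "For each episode, the highest grade attained should be reported".

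**Outputs in SAP 7.1.6.** Two different grade ranges are used for what should be the same group of events:

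- Brief summary, row (2): subjects who "had any Grade 3 or 4 treatment-emergent AE".
- Brief summary, row (4): subjects who "had any Grade 3 or 4 treatment-emergent treatment-related AE".
- Tables by system organ class and preferred term: "All Grade 3 or higher treatment-emergent AEs" and "All Grade 3 or higher treatment-emergent treatment-related AEs".
- By-subject listing: "All Grade 3 and 4 AEs (with a variable indicating whether the event is treatment-emergent, treatment-related, SAE").

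The section also says that, in summaries by severity grade, each subject contributes the most severe event. Deaths are reported in row (9) of the brief summary, in a summary of all deaths, and in a deaths listing flagged for treatment-emergence, relatedness and seriousness. Nothing in the SAP says that Grades 3 and 4 are meant to include Grade 5, or that Grade 5 is left out on purpose.

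**The concern.** On a five-grade scale, a Grade 3 or 4 filter removes fatal events. The headline rows would then leave out the gravest events, while the tables that support them keep those events. A reader who compares row (2) with its table could find two different counts for what looks like the same quantity.

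The discrepancy runs in one direction: it can only lower an arm's high-grade count. Safety and tolerability is a stated secondary objective (SAP 1.1). Protocol 1.5 describes a disease with high mortality and names serious infection and malignancy relapse as events of interest, so fatal adverse events are foreseeable in this population.

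**Working it through.** There is no plan figure to reproduce, because the point rests on definitions. The check sets the definitions side by side and then counts an invented example.

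**Step 1: the grade given to a fatal episode.** Only the highest grade is recorded for each episode (Protocol 7.2.2), so an episode that ends in death is Grade 5 and is not also entered as 3 or 4.

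**Step 2: where that episode is counted.**

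| Output in SAP 7.1.6 | Grades covered | Fatal episode included? |
|---|---|---|
| Row (2), any cause | 3, 4 | No |
| Row (4), related | 3, 4 | No |
| High-grade listing | 3, 4 | No |
| High-grade tables, any cause and related | 3, 4, 5 | Yes |

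Rows (2) and (4) count subjects. A subject therefore drops out of row (2) only if no other treatment-emergent event is Grade 3 or 4, and out of row (4) only if no other related one is. The listing shows events, so every Grade 5 event is absent from it whatever else the subject had.

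**Step 3: an invented set of six subjects** (grade, with R = related and U = unrelated):

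- A: 5R
- B: 3U and 5R
- C: 3R
- D: 4U
- E: 2U
- F: 5U

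| Counting rule | Any cause | Related |
|---|---|---|
| Any Grade 3 or 4 event | 3 (B, C, D) | 1 (C) |
| Most severe event taken first, then kept if Grade 3 or 4 | 2 (C, D) | 1 (C) |
| Grade 3 or higher | 5 (A, B, C, D, F) | 3 (A, B, C) |

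The first two lines differ because of B. If a programmer takes the most severe event before applying the filter, B's separate Grade 3 event no longer counts. The example shows only how the rules behave. It says nothing about the trial's data.

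**Step 4: effect per subject.** The planned arm size is 50 (Protocol 8.9, SAP 1.3). One omitted subject lowers a row by 1/50 = 2.0 percentage points, and three would lower it by 3/50 = 6.0 points.

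**Step 5: can the number of such subjects be bounded?** Protocol 1.1.1 gives a 5-year mortality of 30-50%. Assume a constant hazard, with S the 5-year survival and t in years, so that the proportion dying is 1 − S^(t/5).

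- 48 weeks, t = 48/52.18 = 0.920: S = 0.70 gives 6.4% and S = 0.50 gives 12.0%. Times 50, that is 3.2 to 6.0 deaths per arm.
- Adding the 30 days of the treatment-emergent window (SAP 7.1.5.1), t = 0.920 + 30/365.25 = 1.002: 6.9% and 13.0%, or 3.4 to 6.5 deaths per arm.

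The result depends on the window and on the constant hazard. It also counts all deaths, not subjects whose only high-grade event was fatal. It is background and not a bound.

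**The case against.** **Fatal events are reported elsewhere.** This stands, and it limits the point. Death is a seriousness criterion in Protocol 7.1.2. A treatment-emergent fatal event is therefore counted in rows (1) and (5) and, if related, in rows (3) and (6). It is also in the Grade 3 or higher tables, the deaths summary, the unrestricted adverse-event and serious-event listings, and the flagged deaths listing. A reader might infer that fatal events vanish from the safety report. The documents do not support that. What these outputs leave open is narrower. Row (9) is not restricted by relatedness or to the treatment-emergent window, no row of the brief summary isolates related fatal events, and the row-to-table mismatch remains.

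**The layout could be deliberate.** Showing Grades 3 and 4 apart from deaths is a legitimate choice, but the SAP does not say it was made, and the tables in the same section do not follow it. For laboratory data a Grade 3 and 4 limit is complete, because SAP 7.2.2 stops at Grade 4. For adverse events it is not.

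**Nothing is tested on these counts.** This is also correct. SAP 3.5 rules out formal comparisons after early termination, and the adverse-event outputs are numbers and percentages.

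**An arm with more deaths could look better.** A reader might infer this from row (2). It requires that the subjects who died had no other Grade 3 or 4 event, and the same brief summary would show that arm's deaths in row (9) and its serious events in row (5).

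**Conclusion.** The inconsistency is real and lies within one section of the SAP. Followed as written, rows (2) and (4) can be lower than their supporting tables. They can be lower still if the most-severe-event rule is applied before the grade filter. The listing cannot be reconciled with the tables once any Grade 5 event exists.

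The size is unknown and may be zero. The documents contain no adverse-event data, and the study was stopped early (SAP 2.3), so the planned numbers and follow-up may not apply. A reader might take 3 to 6 subjects per arm as an upper limit from the background mortality. That is not supported: the 30-day window alone moves the range to 3.4 to 6.5, and mortality concentrated early would move it further. The firm statement is 2 percentage points per affected subject at 50 per arm.

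This is a correction to the consistency of a headline safety table. It is not a finding that safety information is withheld. The change is still worth making, because it is specific and it removes an undercount that runs in one direction only.

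**What to change.** In SAP 7.1.6, define rows (2) and (4) of the brief summary as Grade 3 or higher, and define the listing in the same way. Both rows then equal the subject totals of the corresponding tables by definition. In the invented set, they become 5 for any cause and 3 for related events in both places. The order of filtering and selecting the most severe event no longer matters, because a subject's worst event is Grade 3 or above exactly when any event is.

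Optionally, add a row for treatment-emergent adverse events leading to death, overall and treatment-related. If the exclusion of Grade 5 was intended, state it in a footnote that points to the death outputs, and add the treatment-related fatal row.

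The cost is a wording change and a change of filter in the programs. No new data are needed. The reported high-grade percentage may rise slightly.

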5.5. Opportunistic Infections and Prophylactic Regimens

Patients with ongoing cGVHD or continued use of immunosuppressive therapy should be considered as immune deficient and at risk for significant infectious complications. Thus, prophylaxis for opportunistic infection according to institutional treatment standards are mandated. For additional questions please refer to IDSA guidelines {[Tomblyn et al 2009](#)}. Specifically, CMV surveillance is mandated and in case of clinical infection or the need for preemptive CMV treatment, investigational treatment must be discontinued.

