2.3. Final Analysis

Due to early termination of the study by sponsor for lack of efficacy based on the interim futility analysis results, the final analysis of the data will be performed after all enrolled subjects have finished their follow-up/early-termination visit after the last dose of study drug, outstanding data queries have been resolved or adjudicated as unresolvable, and data have been cleaned and finalized.

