3.1.2. Safety Analysis Set

The Safety Analysis Set includes data from all subjects who received at least 1 dose of study drug, with treatment assignments designated according to actual treatment received. All data collected up to earlier of the last dose of study drug plus 30 days or first dose of OLE will be included in the safety summaries. The Safety Analysis Set will be used for analyses and summaries of exposure of study drug, corticosteroids, prior and concomitant medication, laboratory data, vital signs, and AEs.

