4.2.1. Duration of Exposure to Study Drug

Duration of exposure is defined as (last dose date – first dose date + 1), regardless of temporary interruptions in study drug administration, and will be expressed in weeks (recorded to 1 decimal place, eg, 4.5 weeks).

Duration of exposure to study drug will be summarized using descriptive statistics (n, mean, SD, median, Q1, Q3, minimum, and maximum) and as the number and percentage of subjects exposed for at least 4, 8, 12, 24, 36 and 48 weeks.

Summaries will be provided by treatment group for the Safety Analysis Set. No inferential statistics will be provided.

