6.4. Secondary Efficacy Endpoints

6.4.1. Definition of Secondary Efficacy Endpoints

The key secondary endpoints are:

- Change from baseline in the skin domain of the LSS at 24 weeks
- Change from baseline in the mouth domain of the LSS at 24 weeks
- Change from baseline in the eyes domain of the LSS at 24 weeks
- Change from baseline in the total score of the LSS at 24 Weeks

Other secondary endpoints include:

- Duration of response, defined as the time from the documentation of BORR to the documentation of PD as defined in [Table 3](#). Note that a flare does *not* constitute an end to response. A sensitivity analysis for DOR could consider a flare does constitute an end to response.
- Proportion of subjects who ever achieve at least 50% reduction in systemic corticosteroid dose relative to baseline, where % reduction is calculated as (systemic corticosteroid dose at 24 weeks – baseline systemic corticosteroid dose) / baseline systemic corticosteroid dose.
- Proportion of subjects who initiate second-line therapy for cGVHD, defined as receiving any therapy besides systemic corticosteroids or study drug for the treatment of cGVHD. Inhaled and topical steroids are not considered second-line therapy.
- Failure-free survival (FFS), defined as the time from randomization to the earliest of first documentation of systemic therapy change, non-relapse mortality, or recurrent malignancy

- Safety and tolerability of ENTO

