7.1.7. Additional Analysis of Adverse Events

The following categories of AEs of special interest will be summarized (number and percentage) by treatment group.

- Relapse of primary disease/chimerism
- CMV reactivation
- PJP (Pneumocystis Jiroveci Pneumonia)
- EBV reactivation
- Interstitial lung disease

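### Adverse events are tabulated by arm only as n (%) in a window tied to dosing; descriptive subject-year rates and a Week 48 SAE table would be a cheap safeguard if drug stopping differs by arm

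*SAP*

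**What the plan says.** The unit of every by-arm AE summary is the subject, counted once. SAP 7.1.6 provides that "Summaries (n and percentage of subjects) of treatment-emergent AEs (by SOC and PT) will be provided by treatment group using the Safety Analysis Set", and SAP 7.1.7 adds that "The following categories of AEs of special interest will be summarized (number and percentage) by treatment group". Protocol 8.6.2 uses the same measure.

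The window belongs to the individual subject. SAP 7.1.5.1 counts double-blind events with onset "no later than earlier of 30 days after permanent discontinuation of study drug or placebo, or first dose date of ENTO in OLE phase", plus any AE that leads to premature discontinuation. SAP 3.1.2 applies the same closing rule to the safety summaries.

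Several rules close that window:
- For CMV, Protocol 5.5 says that "in case of clinical infection or the need for preemptive CMV treatment, investigational treatment must be discontinued".
- Protocol 7.4.4 calls for permanent discontinuation after a confirmed related Grade 4 event, and 7.4.1 after a related Grade 3 or 4 event that recurs following interruption. A first related Grade 3 event only interrupts dosing (7.4.3).
- Protocol 6.11 allows stopping for unacceptable toxicity, relapse, or cGVHD that needs a disallowed therapy.

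Serious events are collected for longer than they are tabulated. Protocol 7.3 requires SAEs to be reported throughout the study, and 6.5.2 asks subjects who stop drug to keep attending through Week 48. Non-serious AEs are collected only to 30 days after last dose.

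Three provisions partly cover the gap. SAP 4.2.1 tabulates exposure by arm, including "the number and percentage of subjects exposed for at least 4, 8, 12, 24, 36 and 48 weeks". Deaths in SAP 7.1.6 carry no treatment-emergent limit. Failure-free survival (SAP 6.4.1) runs over "time from randomization to the earliest of first documentation of systemic therapy change, non-relapse mortality, or recurrent malignancy".

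**The concern.** With equal observation time in both arms, n (%) is a fair comparison. Here observation time depends on how long the subject stays on drug, and drug is stopped for toxicity, CMV or disease control, any of which could differ between ENTO and placebo. The arm that stops more is watched for less time and so shows fewer late events.

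Events that cluster early are little affected, and the event that causes stopping is counted. What is exposed is an event that accrues steadily and does not itself end dosing. Non-fatal infections are the main case: Protocol 1.5 names serious infections as events of interest, and no by-arm table outside this window covers them. If ENTO were the arm that stops more, part of a real excess of infections could be hidden.

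**Working it through.** **The plan's own figures.** The only planning numbers are in SAP 1.3. Exact enumeration of Fisher's test at 40 per arm, 50% against 80%, gives power 0.749 against the stated 75%, and 40/(1 − 0.20) = 50 per arm. Both reproduce. The point does not depend on them, except that 20% dropout is taken as the base stopping level.

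**Assumed inputs.** Neither document gives an AE rate or a stopping rate by arm for this trial. I take hazards λ of 0.3, 0.6 and 1.0 first events per year, equal in both arms, and 20% to 50% of subjects stopping drug by Week 48.

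**Model.** With a proportion s stopped by Week 48, the weekly stopping rate is k = −ln(1 − s)/48. Mean exposure, capped at 48 weeks, is s/k. The window adds 30 days (4.3 weeks). For s = 0.20, k = 0.2231/48 = 0.00465, mean exposure is 43.0 weeks and the mean window is 47.3. The percentage with an event is the mean of 1 − exp(−λT) over the window T.

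| Stopped by Week 48 | Mean window (weeks) | % with event, λ = 0.3 | λ = 0.6 | λ = 1.0 |
|---|---|---|---|---|
| 20% | 47.3 | 23.6 | 41.4 | 58.4 |
| 30% | 44.7 | 22.4 | 39.3 | 55.7 |
| 40% | 41.9 | 21.1 | 37.2 | 52.9 |
| 50% | 38.9 | 19.7 | 34.9 | 49.9 |

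**False difference with no true effect** (from unrounded values): 1.2 to 2.6 points for 20% against 30% stopping, 2.6 to 5.4 for 20% against 40%, and 2.7 to 5.8 for 30% against 50%.

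**Sensitivity of the 20% against 40% case:**
- All completers enter the open-label extension: 2.2 to 4.8 points.
- 70% of the hazard falls in the first 16 weeks: 1.4 to 2.7.
- A common termination cut, uniform over 0 to 96 weeks: 1.7 to 3.8.

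A gap of only 5 points (20% against 25%) gives 0.6 to 1.3, and equal stopping gives zero.

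**Masking.** Suppose ENTO raises a hazard of 0.6 by half. With 40% of ENTO and 20% of placebo subjects stopping, the table shows 49.5 − 41.4 = 8.1 points. With 20% stopping in both arms it shows 54.7 − 41.4 = 13.3.

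**Sampling error.** For 41.4% against 37.2%, 1.96 × √[p₁(1 − p₁)/n + p₂(1 − p₂)/n] is 19.1 points at 50 per arm, 21.4 at 40 and 24.7 at 30. The SAP does not state the number enrolled.

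**What the rate display does.** At 50 per arm and λ = 0.6, expect 20.7 events in 34.5 subject-years against 18.6 in 31.0, which is 60 per 100 in both arms. The precision is poor: 1.96 × √(20.7/34.5² + 18.6/31.0²) = 0.376, or about 38 per 100.

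**SAE time not tabulated.** Subject-time to Week 48 that falls after last dose + 30 days averages 4.2, 6.4 and 8.8 weeks at 20%, 30% and 40% stopping. Divided by 48, that is 8.7%, 13.3% and 18.2%.

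**The case against.** The strongest reply is that n (%) is the usual display when both arms have the same planned 48 weeks, that it matches the protocol, and that the harm is hypothetical. SAP 2.3 records that the final analysis is run "Due to early termination of the study by sponsor for lack of efficacy", and SAP 3.5 rules out formal comparisons. All of this stands. It limits the point to a descriptive addition, without rate differences or confidence intervals.

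Three stronger readings are tempting, and the documents do not support them.
- **That the planned AE comparison is biased.** Nothing in either document shows unequal exposure. The stopping rules make it possible, no more.
- **That a reader could not adjust the percentages.** SAP 4.2.1 gives mean exposure by arm. Dividing −ln(1 − p) by the mean window in years for the 20% against 40% case at λ = 0.6 gives 58.9 against 57.9 per 100 subject-years, so most of the false gap goes. The hazard ratio of 1.5 is recovered as 1.45. This is a rough correction that needs a constant hazard and ignores open-label entry, but it is available.
- **That CMV reactivation and relapse are the events most understated.** CMV infection or preemptive treatment forces a stop, and relapse is a listed reason to stop. An AE that leads to discontinuation counts as treatment-emergent whatever its date. These events are missed only when something else stops dosing first, and relapse also enters failure-free survival.

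It is also fair to say that rates do not cure informative stopping. With a shared gamma frailty (variance 1) linking stopping and events, at 20% against 40% stopping, the rates are still 45.3 against 42.1 per 100, although Week 48 incidence regardless of stopping is 35.6% in both arms. That is the reason for the second table in the fix.

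**Conclusion.** The point holds as a minor, conditional improvement; it is not an error in the plan. If stopping differs by 10 to 20 points from a 20% base, percentages for steadily accruing AEs shift by about 1 to 5 points in favour of the arm that stops more. The shift is less if events cluster early or termination cuts both arms alike. It rests on assumed hazards and assumed stopping rates, and it is small beside a half-width of 19 to 25 points.

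Two things still justify acting. The bias has a known direction: in the masking example it hides 13.3 − 8.1 = 5.2 points of a real excess. And SAEs are collected after the window but reach only listings, unless fatal or leading to discontinuation.

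**What to change.** Keep the n (%) tables and add two descriptive displays.

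1. In SAP 7.1.6 and 7.1.7, give events, subject-years and first-event rate per 100 subject-years by arm. Time at risk ends at the first event or the close of the double-blind window. Limit this to any treatment-emergent SAE, Grade 3 or higher treatment-emergent AEs, the Infections and infestations SOC, and the special-interest categories. Give no tests or intervals for rate differences, in line with SAP 3.5.
2. Tabulate SAEs by randomised arm from first dose through Week 48, or last study visit if earlier, before any open-label dose. Show the total, and separately first SAEs that start before and after second-line therapy. Restrict it to SAEs, because other AEs are not collected beyond 30 days after last dose.

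The cost is SAP wording and two tables from dates already collected. There are limits to state with them. The rates assume a roughly constant hazard and stopping unrelated to risk. The Week 48 table includes off-drug time and SAEs due to rescue therapy, and it is incomplete for subjects who stop attending. If second-line therapy multiplied a 0.6 SAE hazard by 1.5 to 2 (assumed) and every subject who stopped started it, 20% against 40% stopping would give 43.9% against 45.6%, up to 45.2% against 48.2%. The row before second-line therapy alone would read 38.4% against 34.0% and flatter the arm that stops more, so all rows are needed.
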